5. STUDY OBJECTIVES AND ENDPOINTS

5.1. Primary Objectives

The primary objectives of this study are:

- To evaluate the efficacy of NYX- 2925 taken orally once daily versus placebo for the treatment of fibromyalgia.
- To assess safety and tolerability of NYX-2925 taken orally once daily

5.2. Secondary Objectives

The secondary objective of the study is:

- To assess effects of NYX-2925 taken orally once daily versus placebo on general pain, sleep interference, fatigue, physical functioning, psychological state and global improvement.

5.3. Study Endpoints

5.3.1. Efficacy Endpoints

The primary efficacy endpoint is:

[figure not shown]
- Change from baseline in the weekly mean of the daily Numerical Rating Scale (NRS) score assessing average pain intensity in the past 24 hours

The secondary efficacy endpoints are:

- Percentage of subjects “much improved” or “very much improved” on the Patient Global Impression of Change (PGI-C) at Week 12
- Change from baseline in the weekly mean of the Daily Sleep Interference Scale (DSIS) scores at Week 12
- Percentage of subjects achieving $\geq 30\%$ reduction from baseline in the weekly mean NRS average pain intensity at Week 12
- Percentage of subjects achieving $\geq 50\%$ reduction from baseline in the weekly mean NRS average pain intensity related to fibromyalgia at Week 12
- Change from baseline to Week 12 in the Fibromyalgia Impact Questionnaire – Revised (FIQR) score
- Change from baseline to Week 12 in the Patient Reported Outcomes Measurement Information System – Fibromyalgia (PROMIS_{FM}) sleep disturbance score

- Change from baseline to Week 12 in the Patient Reported Outcomes Measurement Information System – Fibromyalgia (PROMIS_{FM}) fatigue profile score
- Change from baseline to Week 12 in the Patient Reported Outcomes Measurement Information System – Fibromyalgia (PROMIS_{FM}) physical function score
- Cumulative response (percent reduction from baseline) in the weekly mean NRS average pain intensity at Week 12
- Use of rescue medication, including the proportion of subjects using rescue medication, the frequency and amount used
- Change from baseline in the weekly mean of the daily Numerical Rating Scale (NRS) at each week from Week 1 through Week 12

5.3.2. Other Efficacy Endpoints:

5.3.3. Safety Endpoints

[figure not shown]
The safety endpoints will include adverse events, (AE), serious adverse events (SAE), discontinuation due to adverse events and the S-STS.

6. INVESTIGATIONAL PLAN

6.1. Overall Study Design and Plan: Description

This 13- to 16-week study will include a 1- to 4-week Screening Period, followed by a 12-week double-blind, randomized, placebo-controlled Treatment Period (Figure 1). After completion of the study visits, the site will contact the subjects by telephone within 7-10 days to complete a safety follow-up call. The Investigator, at their discretion, may ask subject to return for an Unscheduled Visit for any safety concerns, abnormal laboratory or ECG findings. A final call will be made to the subject approximately 30 days after the final visit to assess for AE closure and any new SAEs. The study will include up to 52 study sites in the United States.

Figure 1 Study Design

* Length of screening period varies, based on prior analgesic washout

** Dosing with NYX-2925 or matching placebo is once daily for 12 weeks

Table 3: Schedule of Procedures

	Study Period	Screening		Baseline		Treatment Period		
		Study Week (Day)	1 to 4 weeks ^a (-28 to -1)	Week 0 ^d (1±2)	Week 2 (14±2)	Week 4 (28±4)	Week 8 (56±4)	Week 12 ^b (84±4)
			Visit 1	Visit 2		Visit 3	Visit 4	Visit 5
Assessment								
Informed consent prior to any study procedure ^c		X						
Assess inclusion/exclusion criteria		X	X ^d					
APR [®] /PRR [®] training via aLearn ^{®c e}		X	X	X	X ^e	X	X	X
Education on appropriate expectations for participation in a clinical study ^e		X	X	X	X	X	X	X
Patient Global Impression of Severity (PGI-S)		X	X					
American College of Rheumatology (ACR) Fibromyalgia Criteria		X						
2016								
Demographic characteristics (age, sex, race, and ethnicity)		X						
Medical history		X						
Height ^w		X						
Body weight ^x		X						
Vital sign measurements (blood pressure and pulse after sitting or lying supine for at least five minutes) ^f		X	X		X	X	X	X
Physical examination ^g		X						
Electrocardiogram after five minutes in supine position ^h		X	X		X	X	X	X
Urine pregnancy test for females of childbearing potential		X	X		X ^h	X ^h	X ^h	X ^h
Drug screen ⁱ		X	X		X	X	X	X
Obtain samples for chemistry, hematology, and urinalysis		X	X		X	X	X	X
Discontinue all concomitant analgesic medication ^j		X						
Dispense handheld electronic diary		X						
Return handheld electronic diary								X
Dispense/re-dispense rescue medication (acetaminophen) ^k		X	X		X	X	X	X
Return rescue medication and perform accountability ^l			X		X	X	X	X

Table 3: Schedule of Procedures (Continued)

Study Period	Screening		Baseline		Treatment Period		
	Study Week	1 to 4 weeks ^a (-28 to -1)	Week 0 ^d (1 ±2)	Week 2 (14 ±2)	Week 4 (28 ±4)	Week 8 (56 ±4)	Week 12 ^b (84 ±4)
Study Visit	Visit 1	Visit 2	Visit 3 ^v	Visit 4	Visit 5	Visit 6	
Record average pain intensity ^m and rescue medication use over past 24 hours at bedtime for each day	X	X	X	X	X	X	X
Randomize eligible subjects		X					
Dispense study drug ^o		X					
Confirm subject takes first dose of study drug (in the clinic)		X					
Confirm study drug dosing each day via handheld device		X	X	X	X	X	X
Return study drug and assess compliance ^l			X	X	X	X	X
Misuse, Abuse, and Diversion Drug Event Reporting System [®] (MADDERS) ^s				X	X	X	X
Record Daily Sleep Interference Scale (DSIS) each morning ⁿ	X	X	X	X	X	X	X
Assess handheld diary compliance		X	X	X	X	X	X
MINI International Neuropsychiatric Interview (MINI)	X		X	X	X	X	X
Fibromyalgia Impact Questionnaire – Revised (FIQR)				X	X	X	X
Patient Reported Outcomes Measurement Information System – Fibromyalgia (PROMIS _{TM}) ^t			X	X	X	X	X
Patient Global Impression of Change (PGI-C) scale					X	X	X
Sheehan Suicidality Tracking Scale (S-STS)	X	X	X ^v	X	X	X	X
Concomitant medications ^q	X	X	X	X	X	X	X
Adverse events ^r	X	X	X	X	X	X	X
Safety follow-up calls							X ^y

^a Subjects will discontinue all concomitant analgesic medications taken for pain related to fibromyalgia. Duration of the period will depend upon the analgesic(s) being discontinued, not to exceed 4 weeks. Subjects not taking any concomitant analgesic medications at Visit 1 may directly begin Week -1 of the Screening Period.

^b ET=Early Termination. Subjects who prematurely discontinue randomized treatment will have Week 12 procedures performed. Diary completion ends the night before the Week 12 visit.

^c Informed consent includes an additional consent for inclusion in a secure, proprietary, research subject database to screen for protocol violators. The main informed consent document may be executed up to 30 days prior to the screening visit. The date the first screening related activity is completed will be considered the subject's screening date. If the subject does not complete the screening visit within 30 days of signing the informed consent document, the subject must be reconsented.

^d Verify subject still meets all inclusion criteria and does not meet any exclusion criteria.

- e Review of these educational materials via the aLearn portal will be repeated for all subjects at each site-based visit, with the exception of the final visit. Training at Visit 3 is per Investigator discretion. Additional refresher training may be administered depending on findings of an ongoing blinded data review (e.g., if pain score variability is increased on a subject or site level).
- f Vital signs will include blood pressure and pulse after at least five minutes of being seated or lying supine and prior to blood sample collection. Vital signs may be repeated up to three (3) times at screening, per the Investigator's discretion with a minimum interval of five (5) minutes between measurements. All vital signs should be recorded in the subject's source documents with the final measurement of vital signs being entered into the eCRF system.
- g A complete physical examination will be performed at Visit 1 and will include a comprehensive neurological examination. A brief physical examination will be performed at Visit 6.
- h If clinically indicated for females of childbearing potential.
- i Samples will be obtained following an 8-hour fast. Visit 1 tests will include HIV screening, hepatitis B screening, hepatitis C screening, and a thyroid panel (TSH, T₃, T₄ and free T₄). A CRP test will be conducted on each chemistry sample collected.
- j Analgesic medications discontinued during the Screening Period cannot be restarted until after the Week 12 Visit has been completed (except NSAIDs taken for pain unrelated to FM as outlined in the protocol).
- k Subjects will be instructed to take no more than 3 g/daily (one to two 500 mg tablets every 6 hours as needed) for pain related to fibromyalgia.
- l Instruct study subjects to bring all used and unused study drug and rescue medication to each study visit for compliance monitoring. At Visit 3, Study drug & rescue medication use and assessment of compliance will be completed by review of daily use entries in the handheld and by subject interview.
- m Numerical Rating Scale of pain intensity (0 = no pain to 10 = worst possible pain) will be completed once daily at bedtime. Daily Sleep Interference Scale (DSIS) will be completed once daily upon awakening.
- n Starting after Visit 1.
- o Starting after Visit 2. Subjects will be instructed to take one capsule of study drug by mouth once daily and confirm they have taken their study drug for the day via their study-issued handheld device each day.
- p Urine drug screen kit for local testing.
- q Includes prior medications taken within the last 30 days.
- r Adverse events will be collected from the time of study drug administration through the last day of the subject's participation in the study. Serious adverse event reporting will begin at the time informed consent is obtained and will end 30 days after last dose of study drug.
- s To be completed by Investigators or qualified Subinvestigators when potential abuse-related events are identified and upon the completion of each subject's participation in the study.
- t Subjects will complete the PROMIS_{FM} sleep disturbance, fatigue profile and physical function short form questionnaires.
- u Screening ECGs will be collected in triplicate (at least two (2) minutes apart). All other ECGs will be single ECGs.
- v Visit Three (3) will be completed by telephone or videoconference. The subject will be asked to complete the printed copy of the S-STS given to them at their Baseline Visit while communicating with the site staff. The staff will review the subject's answers to the S-STS and recommend corrections, only where the form has been completed incorrectly. The completed S-STS source document will be mailed back to the clinic or returned at the next study visit to be filed in the subject's chart and entered into the eCRF system.
- w To be measured without shoes.
- x To be obtained with a calibrated scale and subject must remove shoes and bulky layers of clothes.
- y A safety follow-up call should be completed 7-10 days after Visit 6 completion. Final safety follow-up call to be made 30 (±5 days) days after Visit 6 completion. Investigator may ask subject to return for Unscheduled Visit, as needed.

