Both single-dose and daily repeat-dose toxicology studies have been performed in rats and dogs. The maximum tolerated dose following a single oral exposure is at least 1000 mg/kg in both rats and dogs. After up to 13 weeks of daily oral administration in rats and dogs, the no-observed- effect level (NOEL) was the highest dose tested for rats (1000 mg/kg/day) and the no-observed- adverse-effect level (NOAEL) was 120 mg/kg/day in dogs. There were no adverse findings in rats. In a 42-day, repeat-dose dog study, minimal or mild changes were observed in liver parameters at the high dose of 180 mg/kg/day. Similar changes were observed in the 13-week, repeat-dose dog study at the high dose of 240 mg/kg/day: liver enzyme levels in plasma were increased, and microscopic examination of the liver revealed pigmented material within bile canaliculi and in the cytoplasm of hepatocytes. These changes in liver parameters were partially reversed after a two-week or four-week recovery phase. In the 13-week repeat-dose study in dog, these observations were considered adverse at 240 mg/kg/day; therefore, the NOAEL was 120 mg/kg in dog. Based on the data to date, the plasma levels (exposure) of NYX-2925 at the NOAEL of 120 mg/kg/day in dog, the most sensitive species, is considered to be approximately 70 and 20-fold the human dose of 50 mg and 150 mg, respectively.

As of June 2019, the clinical development program for NYX-2925 includes two completed Phase 1 studies in healthy volunteers, one ongoing, clinically complete Phase 1 study in healthy volunteers, one ongoing, clinically complete Phase 2 study in subjects with diabetic peripheral neuropathy (DPN), and one ongoing, clinically complete Phase 2 study in subjects with fibromyalgia. NYX-2925 exposure includes 154 healthy volunteers, 301 subjects with DPN, and 23 subjects with fibromyalgia.

In NYX-2925-1001, a Phase 1 single and multiple ascending dose safety and tolerability study in healthy volunteers, pharmacokinetic analysis revealed that absorption of NYX-2925 was relatively rapid; peak concentrations were achieved within two hours after dosing and declined in a roughly monophasic manner over 24 hours. The pharmacokinetic profiles were dose-

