7.5. Methods of Birth Control

If heterosexually active and of childbearing potential, female subjects must agree to consistently use a highly effective method of birth control starting at Visit 1, continuing throughout the study, and for 28 days after the last dose of study drug. Methods of highly effective birth control include:

- Oral or parenteral contraceptives
- Intrauterine device (either hormonal or nonhormonal type acceptable)
- Barrier
- Abstinence

Female subjects must agree not to plan to become pregnant or breastfeed starting at Visit 1, during the study and for 28 days after the last dose of study drug. Female subjects must refrain

from donating ova during the study period and for 28 days after final administration of investigational product.

Male subjects must use a highly effective method of birth control and refrain from sexual activity with female sexual partners who do not use a highly effective method of birth control starting at Visit 1 through the last dose of study drug. Male subjects who are not surgically sterilized for ≥ 90 days prior to Visit 1 and are sexually active with a female partner must use a condom with spermicide during the study. Male subjects must refrain from sperm donation during the study and for 90 days after the final administration of investigational product.

All pregnancies (female subjects and female partners of male subjects) occurring during the study must be followed for information regarding the course of pregnancy, delivery, and condition of the newborn. Follow-up should be provided by the investigator to the Sponsor-designated Medical Monitor in a timely manner. When the newborn is healthy, further follow-up is not necessary.

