9.3.5. Clinical Laboratory Assessments

Blood samples for serum chemistry and hematology will be obtained after an eight-hour fast.

The study investigator should monitor subjects during the study for signs of hepatic abnormality potentially meeting the stopping criteria ([Section 11](#)).

The investigator will review clinical laboratory test results as they become available, for determination and documentation of clinical significance (if there are out of range values). The investigative site will contact the medical monitor for any liver function test results that potentially meet the stopping criteria. Possibly drug-related or clinically significant abnormal values of uncertain causality must be repeated. Persistent abnormal laboratory values should be followed at the investigator's discretion. Abnormal liver function tests (specified in [Section 11](#)) must be repeated within 48-72 hours.

Hematology assessments will include hemoglobin, hematocrit, red blood cell count, white blood cell count, differential (neutrophils, lymphocytes, monocytes, eosinophils, and basophils) and platelet count.

Chemistry assessments will include glucose, calcium, electrolytes (sodium, potassium, bicarbonate, chloride), phosphorus, blood urea nitrogen (BUN), creatinine, albumin, total protein, magnesium, alkaline phosphatase (ALP), aspartate aminotransferase (AST), alanine aminotransferase (ALT), lactate dehydrogenase, gamma-glutamyl transferase (GGT), albumin, total bilirubin, direct bilirubin, indirect bilirubin, uric acid, and C-reactive protein (CRP). A thyroid panel (TSH, T3, T4, and free T4) will also be collected at Visit 1.

Qualitative urinalysis will include pH, specific gravity, glucose, ketones, protein, blood, leukocyte esterase, urobilinogen, nitrites, and reflex microscopy.

Abnormal clinical laboratory tests at screening may be repeated, on a case by case basis, after consultation with the Medical Monitor.

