9.4. Safety and Pharmacovigilance

9.4.1. Adverse Events – Relationship to Study Drug

An adverse event is any untoward, undesired, unplanned clinical event in the form of signs, symptoms, disease, or laboratory or physiological observations occurring in a human being participating in a clinical study with an Aptinyx study drug, regardless of causal relationship.

Laboratory abnormalities are not considered adverse events unless they are associated with clinical signs or symptoms or require medical intervention. However, a laboratory abnormality (eg, a clinically significant change detected on clinical chemistry, hematology, or urinalysis results) that is independent from the underlying medical condition and requires medical or surgical intervention, or leads to study drug interruption or discontinuation, must be considered an adverse event.

The causality of each AE should be assessed and classified by the Investigator as “related” or “not related.” An adverse event is considered related if there is a reasonable possibility that the event may have been caused by the study drug under investigation (i.e., there are facts, evidence, or arguments to suggest possible causation). There is also a timely relationship to the administration of the investigational drug and the event follows a known pattern of response for which no alternative cause is present.

Not Related

- There is no reasonable possibility that the study drug under investigation may have caused the event. The event is obviously explained by another cause or the time of occurrence of the AE is not reasonably related to administration of the study medication.

Related

- There is a reasonable possibility that study drug under investigation caused the event (i.e., there are facts, evidence, or arguments to suggest possible causation). There is also a timely relationship to the administration of the investigational drug and the event follows a known pattern of response for which no alternative cause is present.

When an assessment is not provided, the event will be treated as related for purposes of regulatory reporting.

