9.5. Serious Adverse Events

Serious adverse event reporting will begin at the time informed consent is obtained and will end 30 days after the last dose of study drug. SAEs must be reported to the sponsor or designee using the provided form either by email or fax to the following email address or fax number, respectively:

- [REDACTED]

- [REDACTED]

A serious adverse event is any adverse event occurring at any dose that results in any of the following outcomes:

- Death: “Death” is an outcome and is NOT the adverse event. In the event of death, the cause of death should be recorded as the adverse event. The only exception is “sudden death” when the cause is unknown.
- Is a life-threatening experience: Life-threatening adverse events include any adverse drug experience that, in the view of the Investigator, places the subject at immediate risk of death from the reaction as it occurs. It does not include a reaction that, had it occurred in a more serious form, might have caused death.
- Requires inpatient hospitalization or prolongation of existing hospitalization
- Results in a persistent or significant disability/incapacity: Disability is defined as a substantial disruption in a person’s ability to conduct normal life functions.
- Results in a congenital anomaly/birth defect.
- Additionally, important medical events that may not result in death, be life-threatening, or require hospitalization may be considered a serious adverse event when, based upon appropriate medical judgment, they may jeopardize the subject and may require medical or surgical intervention to prevent one of the outcomes listed previously (eg, allergic bronchospasm requiring intensive treatment in an emergency room or at home).

All serious adverse events that result in death or are life threatening, regardless of causal relationship, must be reported to the Sponsor-designated Medical Monitor within 24 hours of the site’s knowledge of the event. A copy of the initial serious adverse event report must be received within one (1) business day.

All other serious adverse events or other events reportable to the United States Food and Drug Administration (FDA) and/or IRB will be forwarded to the Sponsor-designated Medical Monitor within one (1) business day.

Any reported cases of COVID-19 that meet the SAE criteria above should be reported as per the protocol’s defined SAE process.

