9.6. Other Reportable Events

All pregnancies occurring during the study must be followed for information regarding the course of pregnancy, delivery, and condition of the newborn. Follow-up should be provided by the Investigator to the Sponsor-designated Medical Monitor in a timely manner. When the newborn is healthy, further follow-up is not necessary. Male subjects must inform the Investigator if their partner becomes pregnant during the study.

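### The final safety call can come up to 5 days before SAE reporting ends, an asymptomatic Week 12 liver elevation need not be recorded as an AE, and pregnancy collection has no stated end

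*Protocol*

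**What the plan says.** **Call and SAE window.** Table 3, footnote y: "Final safety follow-up call to be made 30 (±5 days) days after Visit 6 completion". Footnote r says that SAE reporting "will end 30 days after last dose of study drug", and Protocol 9.5 says the same ("will end 30 days after the last dose of study drug"). The call is therefore timed from Visit 6 and the reporting window from the last dose. Protocol 6.1 gives the final call two purposes: closing out AEs and finding new SAEs.

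**Liver results.** Protocol 9.4.1: "Laboratory abnormalities are not considered adverse events unless they are associated with clinical signs or symptoms or require medical intervention". It adds that an abnormality leading to interruption or discontinuation of study drug must be an AE. Section 11 withdraws subjects from treatment at stated ALT/AST thresholds and asks for repeat liver tests. Section 9.3.5 makes that repeat mandatory within 48 to 72 hours, then says: "Persistent abnormal laboratory values should be followed at the investigator's discretion". Section 9.4.3.3 asks that AEs be followed until they resolve. The last scheduled laboratory sample is at Week 12 or early termination. After that, a return visit is at the investigator's discretion (6.1, 10.3.3).

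**Pregnancy.** Protocol 9.6: "All pregnancies occurring during the study must be followed for information". Section 7.5 extends this to partners of male subjects. It sets a 28-day post-dose contraception period for women and says: "Male subjects must refrain from sperm donation during the study and for 90 days after the final administration of investigational product". The last scheduled pregnancy test is at Visit 6 (9.3.5), and pregnancy is not among the stated purposes of the final call.

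**The concern.** All three items concern what is captured once dosing ends. This trial gives 12 weeks of drug, whereas Protocol Section 4 describes tolerability at up to four weeks of dosing. What happens at and just after Week 12 is therefore new information.

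If the last scheduled contact comes before the SAE window closes, events in the final days are found only if the subject or site volunteers them. If the AE rule depends on whether there is still drug to stop, the same laboratory result is counted at one visit and may be left out at another, and the AE tables then under-represent the end of treatment. Section 4 gives some reason to care about liver recovery. Of the dog findings it says "These changes in liver parameters were partially reversed after a two-week or four-week recovery phase", and it describes one subject in an earlier study whose GGT was still above range at last evaluation. If the pregnancy period has no end, sites may apply different cut-offs.

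**Working it through.** **1. Call against SAE window**

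Inputs: the call is made *c* = 25 to 35 days after Visit 6 (footnote y), which is 11 permitted days. SAE reporting ends 30 days after the last dose (footnote r, 9.5). Let *g* = Visit 6 date minus last-dose date. The documents do not state *g*, so it is varied.

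Call day after last dose = *c* + *g*. Largest shortfall = max(0, 30 − (25 + *g*)).

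| *g* (days) | Call day after last dose | Largest shortfall (days) | Permitted call days before the cut-off |
|---|---|---|---|
| 0 | 25–35 | 5 | 5 of 11 |
| 1 | 26–36 | 4 | 4 of 11 |
| 3 | 28–38 | 2 | 2 of 11 |
| 5 | 30–40 | 0 | 0 of 11 |

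At *g* = 0 the shortfall is at most 5/30 = 17% of the window.

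Which *g* is realistic? SAP 6.2.8 counts expected dosing days as (Visit 4 − first dose + 1) + (Visit 5 − Visit 4) + (Visit 6 − Visit 5) = Visit 6 − first dose + 1. That total includes both the first-dose date and the Visit 6 date, so a fully compliant completer has *g* = 0. The protocol does not say whether a capsule is taken on the day of Visit 6, so 0 to 1 is a fair range for completers.

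**2. The same liver result at two visits**

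Take a result that meets a Section 11 threshold, with no symptoms and no treatment given.

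- *Week 4 or 8.* Section 11 withdraws the subject from treatment. The discontinuation route in 9.4.1 makes the result an AE. Follow-up to resolution under 9.4.3.3 applies, and the event enters the TEAE tables (SAP 6.12.1).
- *Week 12.* Planned dosing is over, so nothing can be discontinued. The symptom and intervention routes are not met. The result need not be an AE, 9.4.3.3 does not attach, and the TEAE tables omit it.

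What still happens at Week 12: the site contacts the medical monitor about results that may meet the stopping criteria, liver tests are repeated within 48 to 72 hours (9.3.5, Section 11), and the subject appears in the SAP liver listing, which takes anyone with ALT or AST above 3×ULN or bilirubin above 2×ULN (SAP 6.2.25, 6.12.2).

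The only post-Week 12 liver test with a time limit is that repeat, so required observation is about 2 to 3 days. The dog findings were only partly reversed at 14 or 28 days. Under SAP 6.2.11 and 6.2.12, an unscheduled laboratory result from Day 71 on maps to Week 12 and gives way to the scheduled value. A later recovery sample would therefore be listed but not summarised.

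**3. Pregnancy periods**

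With *g* = 0, the earliest permitted call is 28 − 25 = 3 days short of the female 28-day period. The call is 90 − 35 = 55 to 90 − 25 = 65 days short of the 90-day sperm-donation limit. The end of the study, for this purpose, can be read two ways. The stated length of 13 to 16 weeks equals screening plus treatment (1 + 12 and 4 + 12), which ends at Visit 6. Table 3 also schedules the follow-up calls, which would carry the study to about Day 25 to 35 after Visit 6. No passage chooses between them.

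**The case against.** **SAEs.** The duty to report to Day 30 stands whatever the date of the call, and subjects are told to report all adverse events (9.4.2, 9.4.3). The 5-day figure is a worst case: the earliest permitted call and a last dose on the day of Visit 6. Early terminators who stopped at least 5 days before the visit lose nothing. All of this stands. A reader might infer that the SAE window is cut to 25 days, but the documents do not say so. What is shortened is scheduled contact.

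**Liver.** A reader might infer that a Week 12 elevation goes unfollowed and unreported. The documents do not support that. The repeat is mandatory, 9.3.5 also requires a repeat of possibly drug-related values and of clinically significant values of uncertain causality, abnormal laboratory findings are a named reason for an unscheduled visit, and the SAP lists liver results at all timepoints whether or not they are AEs. Nor is Week 12 unique in kind: the symptom and intervention routes stay open there, and a rise at Week 4 or 8 that does not interrupt dosing is not an AE either.

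The evidence for a liver hazard at these doses is also limited. The dog changes arose at 180 and 240 mg/kg/day, and exposure at the 120 mg/kg/day no-adverse-effect level is put at about 70-fold and 20-fold that of 50 mg and 150 mg in humans. The GGT case arose at 200 mg, twice this trial's top dose, and was falling. Section 4 calls notable laboratory results in the four-week study generally comparable across groups. No passage says a delayed signal is likeliest at Week 12. The point therefore rests on uneven recording between visits, not on a demonstrated hazard.

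**Pregnancy.** A reader might infer that post-dose pregnancies are excluded. The text neither excludes nor clearly includes them. The 90-day figure governs sperm donation; it is not stated as a reporting period.

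**Conclusion.** Three limited gaps hold.

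1. For a completer whose last dose is on the Visit 6 date, the last scheduled contact that asks about new SAEs can come up to 5 days before the reporting window closes. This rests on *g* = 0, which SAP 6.2.8 implies but the protocol does not state. At *g* = 1 it is 4 days, and at *g* of 5 or more it is zero.
2. A Section 11-level liver result without symptoms or treatment is an AE at Week 4 or 8 once the drug is stopped, but need not be one at Week 12. It is retested and listed. It is not carried into the TEAE tables, and follow-up past the retest is discretionary. How many subjects this affects cannot be estimated from the documents.
3. Pregnancy collection has no defined end and is not linked to the 28-day and 90-day periods.

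None of these threatens the efficacy analysis. They are inexpensive improvements to safety capture.

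**What to change.** - Reconcile footnote y with footnote r and 9.5, so that the final scheduled contact does not come before the end of the SAE window.
- State in 9.4.1 that a result meeting a Section 11 threshold is recorded as an AE at any visit, including Week 12. The AE tables then treat visits alike, and the existing follow-up rule in 9.4.3.3 applies. No threshold changes.
- Ask the sponsor to define the end of pregnancy collection in 7.5 and 9.6 and to reconcile it with the 28-day and 90-day periods. The male limits in 7.5 also need reconciling: contraception runs through the last dose, condom use runs during the study, and the sperm-donation limit runs 90 days beyond dosing. This review does not say which limit is right.

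The cost is amendment wording, a slightly narrower call window, a few more recorded AEs, and some repeat liver tests in the subjects affected.
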